Planned Analysis: Initial data analysis will include descriptive statistics for all variables, including assessment of potential outliers and the extent of missing data. If the missing data rate is small, < 5%, and found to be at random, then complete case analyses will be performed; otherwise, multiple imputation strategies will be explored. Data will be presented as frequencies for categorical variables and means (standard deviations) for continuous variables. We will compare characteristics between groups using t-tests for quantitative variables and chi-square tests for categorical variables. For the primary outcome, intervention feasibility, we will calculate participants' willingness to enter the trial (percent of eligible Veterans approached who consented to participate), recruitment rate (number of patients randomized divided by the length of the recruitment period, i.e., from the date that recruitment opened to the date of the last randomization). These measures will shed light on the anticipated acceptability of LT4 discontinuation. Finally, we will calculate completion rate for each arm. Secondary outcomes include changes from baseline to 6 months in the ThyPRO Hypothyroid Symptoms and Tiredness scores, EQ-5D, ThyPRO-39 and blood lipids. We will also assess changes in weight, body mass index, blood pressure,

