and pulse. Analysis of covariance (ANCOVA) models will be employed to analyze these outcomes. Baseline measures and gender will be included in the models as covariates. A one-sided t-test will be used to determine whether the mean ThyPRO Hypothyroid Symptoms and Tiredness scores for the real discontinuation group differ from the mean ThyPRO Hypothyroid Symptoms and Tiredness scores of the sham discontinuation group by no more than 14 points. An  $\alpha$ -level of 0.05 will be used to determine the statistical significance of the non-inferiority test for each ThyPRO domain. Failure to reject the null hypothesis will suggest that the QoL measures in the real discontinuation group, on average, are more than 14 points worse than in the sham discontinuation group. This will be considered as evidence against our conjecture that discontinuation does not negatively affect the QoL of patients with SCH. In addition, analyses comparing groups with respect to adverse event rates will be performed using chi-square tests. Analyses will be based on the intention-to-treat principle. Statistical analyses will be done using SAS 9.4 (SAS Institute, Cary, NC).

*Additional details Analysis Plan:* We will add a Biostatistician to the project. They will be hired through an IPA to work on the project. The Biostatistician will be sent the data set by encrypted email and will use computer software on their laptop (non-VA) to complete the analysis. No name, date of birth or SSN will be included in the data set for analysis. Those data points will remain within the VA protected environment.

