*Sample size estimates:* The overarching goals of this pilot trial are to assess the feasibility of a subsequent, full-scale effectiveness trial and to obtain preliminary estimates of effect sizes. Thus, the pilot needs to be large enough to be informative about the feasibility of recruitment/retention and research procedures and to provide enough information on the efficacy of the intervention to justify and inform the planning of a full-scale trial. The primary endpoints of the full-scale RCT will be the ThyPRO Hypothyroid Symptoms scale and Tiredness scale scores. With an estimated standard deviation of 20 for ThyPRO hypothyroid scale score, from a study of patients with autoimmune hypothyroidism, a sample size of 23 Veterans per group will allow us to achieve 80% power using a 5%  $\alpha$ -level to determine statistical significance for a one-sided t-test; accounting for a drop-out rate of less than 10%, a final sample size of 50 patients will be required. This sample size is adequate both to assess feasibility and to obtain preliminary data on effect sizes.

*Participant Compensation:* Participants will be provided compensation for time and travel expenses as a result of participating in the study. The payments will be distributed as follows: (1) \$50 for completion of Baseline Visit, (2) \$50 for completion of Clinic Follow-up 1 (Month 2), (3) \$50 for completion of Clinic Follow-up 2 (Month 6), and (4) \$100 for completion of all study activities and End of Study survey. The participant will be paid within 4-6 weeks after each clinic visit. Payment will be issued by check or by electronic transfer of funds according to local medical center procedures. The participant name, SSN, address and date of visit are required to process the funds. An Internal Revenue Service (IRS) Form 1099 will be generated using the participant's SSN. On a case-by-case basis, the PI may authorize additional compensation to cover the cost of transportation (public transportation or gas mileage estimate).

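### A failed ThyPRO non-inferiority test is to be read as suggesting quality of life is more than 14 points worse, when it shows only that a 14-point worsening was not ruled out

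*Combined protocol and SAP*

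**What the plan says.** All of this is in the combined protocol and SAP.

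- **Outcomes (Planned Analysis).** "Secondary outcomes include changes from baseline to 6 months in the ThyPRO Hypothyroid Symptoms and Tiredness scores", together with other measures. For the secondary outcomes, "Analysis of covariance (ANCOVA) models will be employed to analyze these outcomes", with baseline value and gender as covariates.
- **Test (Planned Analysis).** "A one-sided t-test will be used to determine whether the mean ThyPRO Hypothyroid Symptoms and Tiredness scores for the real discontinuation group differ" by no more than 14 points; alpha is 0.05 for each scale.
- **Reading of a failed test (Planned Analysis).** Sentence 1, where the comparison is with sham discontinuation: "Failure to reject the null hypothesis will suggest that the QoL measures in the real discontinuation group, on average, are more than 14 points worse". Sentence 2: "This will be considered as evidence against our conjecture that discontinuation does not negatively affect the QoL of patients with SCH".
- **Role of the scales (Sample size estimates).** "The primary endpoints of the full-scale RCT will be the ThyPRO Hypothyroid Symptoms scale and Tiredness scale scores". The pilot is also meant "to provide enough information on the efficacy of the intervention to justify and inform the planning of a full-scale trial".

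Nothing elsewhere describes a failed test as inconclusive, and no confidence interval for the between-group difference is planned.

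**The concern.** The null hypothesis is a mean worsening of 14 points or more with real discontinuation. Rejecting it shows non-inferiority. Not rejecting it leaves a 14-point worsening possible, but does not make it the likely explanation of the data.

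Sentence 1 turns an effect that was not excluded into one that is suggested. The test can fail when the observed worsening is well below 14, and the stated reading then contradicts the trial's own estimate. If the estimate is above 14, the reading agrees with it, but a worsening beyond the margin is demonstrated only when the lower confidence limit also exceeds 14.

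Sentence 2 goes further and takes failure as evidence against the conjecture of no negative effect. When the confidence interval includes zero, the data remain compatible with no effect, and that conclusion is not supported.

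The error runs one way: it can overstate harm from stopping LT4, but cannot produce a false non-inferiority claim. At stake is an inconclusive pilot being reported as suggesting a worsening beyond the margin, on the scales that are to be primary in the next trial.

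**Working it through.** **Inputs from the documents.** Margin 14 and one-sided alpha 0.05 (Planned Analysis). SD 20, 23 per group and 80% power (Sample size estimates). The SD is given for one scale only: "With an estimated standard deviation of 20 for ThyPRO hypothyroid scale score". No SD is given for Tiredness, and no baseline correlation for either scale.

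**Assumed.** True differences of 0, 5 and 14 points (positive means worse with real discontinuation); baseline correlation r of 0, 0.5 or 0.7; SD of 15 to 25 for Tiredness.

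**The plan's own figure.** Sample size estimates states no margin. With margin 14, SD 20 and true difference 0, 23 per group gives 75.6% power by the non-central t distribution (76.7% by the normal approximation), not 80%; 26 per group are needed. This is a side observation. Even at 80% power, 1 − 0.80 = 20% of trials with no true effect would fail and receive the planned reading.

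**Thresholds, unadjusted.**

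- SE = 20 × √(2/23) = 5.90
- 90% half-width = t(0.95; 44 df) × SE = 1.680 × 5.898 = 9.91
- Test fails when the observed worsening exceeds 14 − 9.91 = 4.09
- 90% CI lies wholly above zero when it exceeds 9.91
- More than 14 points worse is demonstrated when it exceeds 14 + 9.91 = 23.91

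| Observed worsening | Test | What the data support |
|---|---|---|
| below 4.1 | passes | non-inferiority |
| 4.1 to 9.9 | fails | estimate below 14, CI includes zero: both sentences wrong |
| 9.9 to 14 | fails | some worsening, estimate below 14: sentence 1 wrong |
| 14 to 23.9 | fails | sentence 1 agrees with the estimate but is not demonstrated |
| above 23.9 | fails | more than 14 points worse |

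Example: an observed worsening of 5 has a 90% CI of 5 ± 9.9, or −4.9 to 14.9. The test fails, and the plan would read this as suggesting more than 14.

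**How often this happens.** Failure probabilities come from the non-central t distribution. The shares among failures come from 2,000,000 simulated trials per case, with the SE estimated in each trial.

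| SD, r | True difference | Fails | Of failures: observed below 14 | Of failures: CI includes zero |
|---|---|---|---|---|
| 20, 0 | 0 | 24% | 96% | 80% |
| 20, 0 | 5 | 56% | 89% | 63% |
| 20, 0 | 14 | 95% | 47% | 20% |
| 20, 0.5 | 0 | 15% | 98% | 66% |
| 20, 0.5 | 5 | 46% | 92% | 47% |
| 20, 0.7 | 0 | 5% | 99% | 30% |
| 20, 0.7 | 5 | 32% | 95% | 17% |
| 15, 0 | 0 | 7% | 99% | 41% |
| 25, 0 | 0 | 41% | 93% | 88% |

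Arithmetic check for the first row: P(observed > 14) = 0.0088, and effectively every such trial fails, so the share of failures below 14 is (0.2444 − 0.0088) / 0.2444 = 0.964.

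The adjusted rows use SD × √(1 − r²). For r = 0.5 the SE is 5.11 and the half-width 8.58, so failure starts at 5.4 and the CI clears zero at 8.6. For r = 0.7 the SE is 4.21 and the half-width 7.08, giving 6.9 and 7.1. That last band is narrow because it fixes the SE at its expected value; the 30% share arises because the estimated SE varies between trials. Using 42 df for the two covariates changes the r = 0.5 failure rate at zero only from 0.146 to 0.147.

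**The case against.** The case for leaving the text alone has four parts.

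1. **The wording is hedged.** The plan says failure suggests a worsening; it does not say failure demonstrates one. For observed worsening above 14 that is fair, since the estimate does point that way. It does not help below 14, where the reading contradicts the estimate. At an observed 5 with SE 5.90, a normal likelihood favours a true difference of 0 over 14 by exp[(9² − 5²) / (2 × 5.898²)] ≈ 2.2 to 1.

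2. **Failure is some evidence of harm.** Unadjusted, it is 0.95 / 0.244 ≈ 3.9 times as likely at a true difference of 14 as at 0. This is correct for the bare fact of failure, so sentence 2 is not empty. But the trial will have an estimate and its precision, and those supersede the pass/fail label. If the interval includes zero, the standard reading is that the result is inconclusive about any worsening.

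3. **The figures depend on the assumed truth, and adjustment will help.** Both points stand. At a true difference of 14, only 47% of failures fall below 14. Baseline adjustment makes failure rarer and shrinks the sentence-2 problem considerably. It does not correct sentence 1: at a true difference of 0, 98% to 99% of the remaining failures still have an observed worsening below 14.

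4. **The reach is limited.** ThyPRO is secondary, no go/no-go rule uses the label, and planning of the full trial can rest on the effect estimates. All true. This limits the severity but does not make the stated rule right.

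**Conclusion.** The concern holds. Followed as written, the plan draws a wrong conclusion from a failed test whenever the observed worsening lies between the failure threshold and 14, and sentence 2 is also unsupported whenever the 90% CI includes zero. With SD 20, 23 per group and no adjustment, those ranges are 4.1 to 14 and 4.1 to 9.9 points. At a true difference of 0 the test fails 24% of the time, and 96% of those failures carry a reading that contradicts the estimate.

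The logical error depends on no assumption. Its frequency depends on the SD, the baseline correlation and the true difference: at a true difference of 0, failure runs from 5% (SD 20, r = 0.7) to 41% (SD 25, unadjusted) across the cases tabulated. This should be fixed, with limited reach: the primary feasibility outcome, the test, the margin and the estimates stand.

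**What to change.** Replace the two interpretive sentences in Planned Analysis with text such as:

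> For each scale, the between-group difference at 6 months (positive means worse with real discontinuation) will be estimated from the planned ANCOVA, which also supplies the one-sided 5% non-inferiority test, and reported with its two-sided 90% CI. If the upper limit is below 14, non-inferiority is shown. If it is 14 or above, non-inferiority is not shown: a mean worsening of 14 points or more was not ruled out. In either case we will state whether the CI lies wholly above zero (evidence of some worsening, against the conjecture of no negative effect), includes zero (inconclusive about any worsening) or lies wholly below zero. A worsening of more than 14 points will be concluded only if the lower limit exceeds 14.

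The check against zero applies to every result because a non-inferior result can still show some worsening. For example, with an assumed SD of 15 and r = 0.5 the half-width is 6.4, so an observed 7 gives a 90% CI of 0.6 to 13.4. Naming the ANCOVA also settles whether the test comes from that model or from a separate t-test, which the section does not state outright.

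The cost is one short paragraph in place of two sentences. The ANCOVA is already planned and its output gives the 90% CI, so no further patients, visits or data are needed.

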*Compliance and Withdrawal:* We will provide an **IRB-approved pill diary** to all study participants. The study team will assess study medication compliance throughout the study. The pill diary may be reviewed at the follow-up clinic visits. Study medication compliance will be considered good if the participant reports taking study medication 80-100% of the time. **Participants may decide not to continue the study medication (LT4 or placebo) at any time. Additionally, the PI may decide not to continue the study medication for an individual (for example, following lab results). We will assist the participant to ensure that appropriate medication, if any, is started at the time of study medication discontinuation. If this occurs, the participant will be asked if they will continue the study (including follow-up visits, blood collection and study questionnaires) without continuing the study medication. If the participant agrees, they will be followed per protocol. If the participant does not agree, they will be classified as withdrawn from the study. We will document this occurrence, reason for discontinuation of study medication and participant decision to continue participation in the study (visits, blood collection and study questionnaires). Participants may agree to all or some of the study procedures.** We will instruct participants who discontinue the study

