**Study Medication Discontinuation Criteria:** The Unblinded Personnel will notify Blinded Study Personnel (SC) if a participant develops OH or hyperthyroidism. At which point, the SC will be unblinded. Results will be communicated to participants and treating physicians by Unblinded Study Personnel and/or SC. The participant will be followed per protocol (following discontinuation of study medication) unless they decide to withdraw from the study at the time of study medication discontinuation. Lab criteria for study medication discontinuation: (1) TSH  $> 10$  mIU/mL or (2) TSH  $< 0.34$  mIU/mL or (3) FT4  $< 0.47$  ng/mL or (4) FT4  $> 1.41$  ng/mL. Study medication will be discontinued if any of the criteria are met. Unblinded Study Personnel will maintain a document for each participant with the Month 2 lab results. The document details the criteria for study medication discontinuation and process of notification. The document will be stored in the Unblinded Study Personnel binder in the Research Pharmacy office (a locked, private office) inside the Outpatient Pharmacy area (locked, private area). The SC will collect a copy of the document from Unblinded Study Personnel once the participant completes the study. The copy will be maintained in the participant folder in a locked file cabinet in a private office. The PI will not be alerted to study medication discontinuation. She may inadvertently become aware of study medication discontinuation, but she will not be informed of the reason (hypothyroidism or hyperthyroidism at Month 2) in order to maintain the blind through the planned analysis. Study medication may also be discontinued in the case of early termination (participant decision to withdraw, Investigator decision to withdraw or joint decision). In this case, the PI may be alerted to study medication discontinuation and study medication assignment.

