The risks involved with discontinuation of LT4 (participants allocated to placebo) include development or worsening of hypothyroidism-related symptoms such as weight gain, fatigue, cold intolerance, body aches, muscle weakness, edema, depression, constipation, hair loss, dry skin, brittle nails, menstrual abnormalities, neck pain/discomfort, memory trouble and cognition issues. In patients with SCH, these clinical manifestations are usually mild. However, given the evidence that LT4 therapy does not confer important hypothyroid-symptom-related benefits for patients with SCH, it is unlikely that the participants who discontinue LT4 will experience the onset or worsening of hypothyroidism-related symptoms. Participants will be informed of this risk and the array of hypothyroidism-related symptoms. We will be monitoring for these side effects during the clinic visits and monthly phone calls and participants will be instructed to notify the PI or research coordinator if they experience these symptoms. Participants may return to the medication they were using before the study, at any time and for any reason. The PI will also discontinue study medication if ongoing treatment becomes inappropriate for the participant.

Fluctuating thyroid hormone levels may be harmful to a fetus. Because of this risk, women who are pregnant or plan to become pregnant are not eligible to take part in this study. We will ask women of child-bearing potential to use birth control for the duration of the study. Acceptable methods of birth control are: (1) hormonal methods, such as birth control pills, patches, injections, vaginal ring, or implants, (2) barrier methods, such as a condom or diaphragm, used with spermicide (a foam, cream, or gel that kills sperm), (3) intrauterine devices, and (4) abstinence (no sex). Women will be instructed to

notify the study team immediately if they miss a period or think they might be pregnant during the study. The PI may ask for permission to collect information about the outcome of the pregnancy.

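### Intention-to-treat is the only basis for the ThyPRO non-inferiority test although placebo participants may return to LT4 and still be scored; alone it supports a claim about assignment to discontinuation, not about staying off LT4.

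*Combined protocol and SAP*

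**What the plan says.** In the combined protocol and SAP, the Planned Analysis sets a one-sided t-test with a 14-point margin and alpha 0.05 for each of the ThyPRO Hypothyroid Symptoms and Tiredness scales. The only analysis basis named is "Analyses will be based on the intention-to-treat principle". A failed test is to count as evidence against "our conjecture that discontinuation does not negatively affect the QoL of patients with SCH".

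Other sections allow treatment to change while follow-up continues:

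- Safety Considerations: "Participants may return to the medication they were using before the study, at any time and for any reason".
- Compliance and Withdrawal: a participant who stops study medication is helped to start appropriate medication, if any, and is asked to stay for visits and questionnaires. "If the participant agrees, they will be followed per protocol".
- Study Medication Discontinuation Criteria, for stops on Month 2 laboratory results: "The participant will be followed per protocol (following discontinuation of study medication) unless they decide to withdraw from the study".

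The plan already records much of what is needed. Compliance is assessed at each scheduled follow-up contact, with 80–100% self-reported intake classed as good. For stops, the team documents the "reason for discontinuation of study medication and participant decision to continue participation in the study". The Planned Analysis adds that "Initial data analysis will include descriptive statistics for all variables", promises a completion rate per arm, and says that if missing data are not both few and at random, "multiple imputation strategies will be explored". No per-protocol, on-treatment or other supplementary analysis appears, and no persistence measure is tied to the non-inferiority test.

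**The concern.** In a superiority trial, dilution from treatment changes usually makes a positive finding harder to reach. In a non-inferiority trial it can make the hoped-for finding easier. A placebo participant who feels worse, restarts LT4 and recovers by Month 6 is scored as a discontinuation participant who did well. Intention-to-treat alone cannot separate two explanations of a small difference: stopping LT4 was harmless, or those harmed by stopping restarted.

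This matters beyond the pilot. The ThyPRO scales are secondary outcomes here, but Sample size estimates uses them to size the trial, names them as primary endpoints of the full-scale trial, and wants the pilot to help justify and plan that trial. A diluted difference would carry into that planning.

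**Working it through.** **Inputs from the documents.** Margin 14 and one-sided alpha 0.05 (Planned Analysis); SD 20, 23 per group, 50 in total (Sample size estimates); 1:1 allocation (Randomization Scheme), hence 25 per arm.

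**Assumptions.** The return rate is not given. I take k = 3, 5 or 8 of 25 placebo participants back on LT4 by Month 6, so f = 0.12, 0.20 or 0.32. How far returners regain LT4-arm scores, and who returns, are also assumed and varied below.

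**The plan's own figure.** With margin 14, SD 20, true difference 0 and one-sided alpha 0.05, 80% power needs 26 per group, not 23. Power by the t-test is 75.6% at 23 per group and 78.7% at 25. That is a separate matter; the present point does not depend on it.

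**Decision rule with 25 per arm.** SE = 20 × √(2/25) = 5.657. Non-inferiority is declared when (difference − 14)/SE < −t(0.95, 48) = −1.677, so when the difference is below 14 − 1.677 × 5.657 = 4.51 points.

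**Dilution.** If staying off LT4 truly costs 14 points and returners fully regain LT4-arm scores, the intention-to-treat difference is 14 × (1 − f): 12.3, 11.2 and 9.5 points. Put the other way, a 14-point margin on that difference corresponds to 14/(1 − f) = 15.9, 17.5 and 20.6 points for staying off LT4.

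**Chance of declaring non-inferiority when staying off LT4 truly costs 14 points** (5% with no returns):

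| Scenario | k = 3 | k = 5 | k = 8 |
|---|---|---|---|
| Noncentral t, mean shift only | 8.8% | 12.4% | 19.4% |
| Simulation, return unrelated to score, full regain | 8.6% | 11.7% | 18.2% |
| Same, half regained | 6.7% | 7.9% | 10.3% |
| Same, full regain, residual SD 17.3 (ANCOVA, assumed baseline correlation 0.5) | 9.0% | 13.0% | 21.3% |
| Worst-scoring placebo participants return | 10.4% | 15.6% | 24.5% |

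**Two simple remedies, checked where the worst scorers return:**

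| Analysis | k = 3 | k = 5 | k = 8 |
|---|---|---|---|
| Intention-to-treat alone | about 10% | 15% | 25% |
| Returners dropped | 21% | 34% | 55% |
| Returners imputed once at LT4-arm prediction + 14, alone | about 14% | 20% | 23% |
| That imputation and intention-to-treat both required | about 10% | 14% | 19% |

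Dropping returners is clearly worse than intention-to-treat. The fixed imputation is cautious when return is unrelated to scores (false non-inferiority 3.2%, 2.0%, 0.8%). It fails when the worst scorers return: they would have scored well above the LT4-arm prediction plus 14, and the placebo scores left in place are selectively good.

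**The case against.** Intention-to-treat is a legitimate basis. Sample size estimates describes the later study as an effectiveness trial, and the protocol defines real discontinuation as allocation to placebo. Assignment with return allowed is then a natural question. Some returns would follow laboratory stops that the protocol itself requires, so for those participants remaining on assigned treatment is not an option under the plan. This stands, and it is why the intention-to-treat test should stay.

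The Planned Analysis spells out only what a failed test would mean; the positive conclusion about discontinuation is implied. That also stands, but the conjecture is worded about discontinuation itself, and a successful test would naturally be read as supporting it.

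A reader might infer that every return biases the result toward non-inferiority, and from the placebo side only. The documents do not support that. The shift needs a true harm that resuming LT4 reverses; with no true effect none is expected. Exposure in the LT4 arm can change too: the laboratory criteria also stop study medication for low TSH or high FT4, and replacement medication is given only if appropriate.

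A reader might also infer that the plan ignores persistence. It does not: compliance, stops and reasons are recorded. What is missing is their use beside this test. The completion rate is undefined, and a participant back on LT4 who attends Month 6 could count as a completer.

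**Conclusion.** The point holds in conditional form. Intention-to-treat validly tests whether assignment to discontinuation, with return to LT4 allowed, is non-inferior. Alone it cannot support the conjecture that discontinuation itself leaves quality of life unharmed.

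With 3, 5 or 8 of 25 placebo participants returning, false non-inferiority for staying off LT4 is about 8–9%, 12% and 18–19%, or about 10%, 15% and 25% if the worst scorers return, against a nominal 5%. These figures rest on an assumed return rate, full regain after return, SD 20, 25 per arm and a true deficit of exactly 14 points. With few returns the effect is negligible. The stronger reading, that the planned test is invalid or must be replaced, is not supported. Because the scales are secondary outcomes of a 50-person feasibility pilot, this is something to consider rather than a required correction.

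**What to change.** 1. Keep the intention-to-treat test, and word its conclusion as assignment to discontinuation with return to LT4 allowed.
2. Beside the test, tabulate by arm the proportion still on assigned study medication at Month 6 and the proportion back on LT4, using the compliance, stop and reason data already recorded. Show unknown status separately.
3. Pre-specify one supplementary sensitivity analysis per scale. Set aside placebo-arm Month 6 scores obtained after return to LT4. Multiply impute them using baseline and any Month 2 ThyPRO score taken before return, with a penalty that increases from 14 points above the LT4-arm prediction. Report the penalty at which non-inferiority is lost. Claim that discontinuation itself is non-inferior only if the result survives penalties judged plausible in advance.
4. Do not drop returners, and do not rely on a single fixed imputation at the LT4-arm prediction plus 14.

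The cost is a paragraph in the analysis plan and a further run of the model, with imputation the plan already foresees. Power for the stronger claim falls: at a penalty of 14, with no true difference and return unrelated to scores, it is about 67%, 58% and 38% with 3, 5 and 8 returns, against 79% with none. Higher penalties lower it further. The source forms are not in these documents, so confirm that they record whether and when LT4 was restarted. No change to the return or stopping rules is suggested.

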Randomization Scheme: 1:1, a randomized block design will be implemented to ensure group sizes are equal. Block sizes of 2, 4, and 6 will be used. In addition, randomization will be stratified by participant's pre-study dose of LT4.

Blinded Person(s): PI, Co-Investigators (Drs. [name], [name]), Research Coordinator/Study Staff (SC), Participant, participant's other clinicians (routine care), Biostatistician, Safety Monitor

Unblinded Person(s): [name] (Co-Investigator and Research Pharmacist), [name] (Research Staff and Research Pharmacy), [name] (Research Staff and Pharmacist)

Study Medication Blinding Procedure: The brand of LT4 to be used in this study will be Synthroid® tablets of 25 mcg, 50 mcg, and 75 mcg (AbbVie Inc). The study drugs (LT4 and placebo) will be sourced, assembled, and packaged by the CAVHS Research Pharmacy. Over-encapsulation will be achieved using a capsule filler and will ensure that capsules are kept as small as possible for the ease of swallowing (DB capsules gelatin size AA, color: White Opaque, manufacturer: Capsugel).

Study Medication Dosing: Participants will be instructed to start the study medication the day after randomization. The study medication will be taken orally once a day. A two-month supply of study medication will be provided to the participant at (1) Baseline, (2) around the time of Clinic Follow-up 1, and (3) around the time of Telephone Visit 3 (Month 4). Study medication may also be provided (in-person or by mail) at an unscheduled visit for reasons such as loss of study medication or resupply.

Source of Information: CAVHS veterans

Use of Information: Evaluate the feasibility of LT4 discontinuation among veterans with SCH and determine changes in quality-of-life measures, blood lipids and adverse events.

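### The stated 80% power does not follow from the plan's own figures: 23 per arm gives about 76% for a one-sided t-test with a 14-point margin and SD 20

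*Combined protocol and SAP*

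**What the plan says.** The calculation is in the paragraph headed Sample size estimates. It starts from "With an estimated standard deviation of 20 for ThyPRO hypothyroid scale score", taken from a study of patients with autoimmune hypothyroidism. It then states that "a sample size of 23 Veterans per group will allow us to achieve 80% power", using a 5% "level to determine statistical significance for a one-sided t-test". The total of 50 follows after "accounting for a drop-out rate of less than 10" percent. The paragraph names neither a difference to be detected or excluded nor an assumed true difference.

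Planned Analysis describes the test. A one-sided t-test asks whether the mean ThyPRO Hypothyroid Symptoms and Tiredness scores under real discontinuation differ from those "of the sham discontinuation group by no more than 14 points". The alpha "level of 0.05 will be used to determine the statistical significance of the non-inferiority test for each ThyPRO domain". The same section plans ANCOVA for the secondary outcomes, with baseline values and gender as covariates. No baseline to follow-up correlation is given anywhere. Allocation is 1:1 (Randomization Scheme).

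Both ThyPRO scales are named as primary endpoints of the later full-scale trial. An SD is given only for the hypothyroid scale.

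**The concern.** Power cannot be computed without a difference, and the sample size paragraph supplies none. Taking the document's only margin, the stated power and the stated group size do not agree.

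The power sentence is the only numerical derivation of the 50 patients, and the pilot is meant to inform a full-scale trial, so a wrong figure or an unstated input can carry forward. It also sets what a reader expects of the non-inferiority tests. Planned Analysis treats a test that fails to reject as a sign that discontinuation is more than 14 points worse. If there is truly no difference, that reading would be wrong in about 24% of trials per scale, not the 20% that 80% power implies.

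The calculation also covers one scale, although two are tested.

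**Working it through.** **Inputs from the document**

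- SD = 20; n = 23 per group; one-sided t-test at 5%; claimed power 80% (Sample size estimates)
- Margin = 14 points; alpha 0.05 for each scale (Planned Analysis)
- Allocation 1:1 (Randomization Scheme)

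**Assumption:** true difference = 0. The document states none.

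**1. Attempt to reproduce 80% at 23 per group**

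Standard error of the difference = 20 × √(2/23) = 5.898.

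Non-centrality = 14 / 5.898 = 2.374, with 23 + 23 − 2 = 44 degrees of freedom and one-sided 5% critical value 1.680.

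- Non-central t: P(T > 1.680) = **75.6%**
- Normal approximation: Φ(2.374 − 1.645) = Φ(0.729) = **76.7%**

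Neither is 80%.

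**2. Sample size needed for 80%**

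n = 2 × [20 × (1.645 + 0.842) / 14]² = 25.2, so **26 per group**. The t calculation agrees:

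| n per group | Power (t) | Power (normal) |
|---|---|---|
| 22 | 73.9% | 75.1% |
| 23 | 75.6% | 76.7% |
| 24 | 77.2% | 78.2% |
| 25 | 78.7% | 79.7% |
| 26 | 80.1% | 81.0% |

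The row for 25 is the case of no loss from 50. With 10% loss, 50 × 0.90 = 45 evaluable (22 and 23), and power is 74.7% (t).

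**3. The dropout step**

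46 / (1 − 0.08) = 50, which fits the stated allowance of under 10%. The mismatch is therefore in the power figure or in an input that is not stated.

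**4. Other readings that might give 80% at 23 per group**

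- Two-sided 5% (equivalently one-sided 2.5%): 64.1%. Further away.
- A true worsening of 2 points leaves 12 points of room: 64.0%. A worsening of 3 points: 57.6%. Further away.
- Solving for the margin at SD 20: about 14.9. A 15-point margin gives 78.9% with 22 per group and 80.5% with 23, so 23 would be the smallest n that reaches 80%. No 15-point margin appears in the document, so whether it is the source of the 23 is a guess.
- Solving for the SD at margin 14: about 18.8.
- ANCOVA, with residual SD = 20 × √(1 − r²), where r is the correlation between baseline and Month 6:

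| r | Residual SD | Power at 23 per group |
|---|---|---|
| 0.2 | 19.6 | 77% |
| 0.3 | 19.1 | 79% |
| 0.35 | 18.7 | 80% |
| 0.4 | 18.3 | 82% |
| 0.5 | 17.3 | 85% |

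Charging a few degrees of freedom for covariates changes these by about 0.1 percentage point.

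**5. Two scales (sensitivity only)**

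If both scales had to pass, with SD 20 assumed for Tiredness as well, joint power at 23 per group would be 0.756² = 57% at zero between-scale correlation. By simulation it rises to about 68% at a correlation of 0.8. The plan does not say that both must pass.

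**The case against.** The strongest reply concerns weight rather than arithmetic. This is a pilot. Its primary outcome is feasibility, the ThyPRO comparisons are secondary, and the sample size paragraph also rests the 50 on feasibility and preliminary effect sizes, neither of which depends on 80% power. With all 50 evaluable the shortfall is about one percentage point. That stands: the error is small, and it does not call for more patients.

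A second reply is that not every input is stated. The margin comes from another section and the zero true difference is supplied here. This is fair, and the fault can equally be called an incomplete calculation. But 14 is the only margin in the document, and any true worsening on discontinuation lowers power further.

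A third is that the planned ANCOVA may well reach 80%. It may, and that limits the practical consequence. It does not support the sentence as written, which cites a t-test and gives no correlation.

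Finally, reading a failed non-inferiority test as evidence of harm is wrong at any power. That is a separate defect, to which the power error adds only about 4 points of false failure. The joint-power figures likewise are not an error in the plan, since no rule requires both scales to pass.

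**Conclusion.** The concern holds: the power sentence is wrong as written. With SD 20, a 14-point margin, one-sided alpha 0.05 and a true difference of zero, 23 per group gives about 76% power per scale. The overstatement is 4.4 percentage points by the t calculation and 3.3 by the normal approximation, equivalent to 3 patients per arm. No standard variant using only the document's figures gives 80% at 23.

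The conclusion rests on two readings: that the 14-point margin is the one meant, and that the true difference is zero. An ANCOVA basis with a correlation of about 0.35 or more would support 80%, but only if it is stated. The Tiredness scale has no stated power basis. The consequence is modest, because the affected tests are secondary and feasibility does not depend on this figure.

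**What to change.** Replace the power sentence with one that shows every input, for example:

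> With an SD of 20, a non-inferiority margin of 14 points, a true difference of zero and a one-sided alpha of 0.05, 23 evaluable participants per group give about 76% power for each scale (about 79% if all 50 are evaluable).

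Alternatively, base the calculation on the ANCOVA already planned and state the assumed baseline to Month 6 correlation with its source; about 0.35 or more supports 80% with 23 per group. If a margin other than 14 was used for sizing, reconcile it with the margin in Planned Analysis.

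In either case, state the SD assumed for Tiredness, and say that the power applies to each scale separately.

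The cost is a sentence or two. N stays at 50, and the stated power becomes slightly less favourable unless the ANCOVA basis is adopted and justified.
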